effects. In addition, preemptive testing allows genotyping samples from many patients to be batched and run in high volume, which substantially decreases the genotyping cost per patient. Thus, the most feasible/sustainable way to facilitate the clinical implementation of PGx in underserved patients will likely involve preemptive genotyping.

To our knowledge, there have been no studies reporting implementation data of preemptive PGx testing in medically underserved patients. Further, there are few data in the literature regarding the perceptions and attitudes of black and Latino patients toward preemptive PGx testing. This work is significant because it is expected to contribute valuable data toward both the feasibility of preemptive PGx testing in medically underserved patients, an area of PGx research where little information is available. We anticipate these data will inform future multi-site clinical trials of preemptive PGx implementation.

5. Specific Aims:

Motivated by the critical need to expand access of preemptive PGx testing to underserved populations, the overall objective for this application is to develop key feasibility data to equitably advance preemptive PGx testing within UF Health, and to generate important preliminary data to support future funding applications. The rationale for this project is that generating these feasibility data should facilitate equitable clinical implementation that may reduce medication treatment disparities, as well as inform future larger clinical studies. We plan to accomplish the overall objective of this application by pursuing three specific aims:

1. Assess the feasibility of preemptive PGx clinical implementation in primary care clinics predominantly serving medically underserved patients. We will provide clinical preemptive PGx testing for 100 patients from specific UF Health clinics serving mostly medically underserved patients, including clinics with a high rate of black and Latino patients. We will assess feasibility of this implementation effort by comparing patient-reported outcomes data abstracted from electronic health records before and 6 months after PGx testing.

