2. Understand perspectives on preemptive PGx testing among key stakeholders in the primary care clinics predominantly serving medically underserved patients. We will conduct in-depth, semi-structured interviews with a subsample of recruited patients from Aim 1 and clinicians within the clinic sites to identify influential factors critical to implementing PGx testing, including motivations, barriers, and best practices for the delivery of results.

3. Identify specific socioeconomic characteristics most strongly associated with PGx drug prescription rates. Our preliminary data using EHR data from UF Health show strong correlations between zip code-derived healthcare geographic access scores and rate of PGx drug prescriptions. We aim to use the results of a validated socioeconomic estimation tool as well as individual measures of socioeconomic status in a single predictive model to determine which social determinants most associate with PGx drug prescription rate within the 100 patients from Aim 1.

6. Research Plan:

Study population and setting. This study will include UF Health patients recruited from clinics that serve mostly medically underserved areas. Primarily, this will include the UF Health Family Medicine Eastside and Main St. Clinics, which serve a large number of low-income, black and Latino patients. Overall, we plan to recruit 100 patients from targeted clinics. Inclusion criteria are designed to identify patients who have a high possibility of benefitting from PGx testing.

Inclusion Criteria:

1. Adults (18 years or older) with active prescriptions for at least 3 medications documented within the EHR.
2. At least 1 drug/drug class that could be informed by the PGx test panel (See Appendix A for complete list).
3. A medication change within the past 6 months (associated with a healthcare provider encounter)
4. Self-identify as black or Latino.

Exclusion Criteria:

1. Patients with any history of PGx testing within the EHR.

Participant Recruitment Methods.

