Patients may be approached for the study in various way including clinic intercepts, study flyers and clinic referrals. The electronic health record will be queried to identify potentially eligible participants using the inclusion/exclusion criteria. Providers (including but not limited to physicians, nurse practitioners, and pharmacists) who care for patients at UF Health will be notified when their patients qualify for the study and will be asked to discuss the study with their patients.

Patients can be recruited by study staff via two methods:

1. Clinic providers or staff ask patients if they are interested in participating and they acknowledge that they are interested.
2. Clinic provider or staff will provide patients an approved flyer and they contact study staff if interested.

If recruitment occurs during a clinic visit, patients meeting eligibility criteria will be approached by a research coordinator about study participation. Patients may also be contacted via phone after their clinic visit if in-person contact is not possible (for example, but not limited to, space limitations due to COVID-19 restrictions).

A research coordinator will review the consent document with the patient prior to enrollment. The consenting process can be in-person or remote via telephone or through electronic means. Prospective research participants will have the opportunity to ask questions before providing consent and will be provided with a signed copy of the consent form.

After providing written informed consent, a DNA sample will be collected from all patients by saliva (via mouthwash swish and expectorate collection) or buccal cell (via buccal brush/swab). If the genotyping fails with initial sample collection, the patients may be mailed a DNA collection kit for saliva or buccal cell sample collection for retesting.

Study design. After eligible participants provide written informed consent and are enrolled, a DNA sample will be obtained for PGx testing and questionnaires (as described below) will be administered at baseline, and then again at 3 months and 6 months after PGx results are entered into the EHR. Information will be abstracted from the EHR including PGx test results, medication changes, and healthcare provider encounters over the 6-month study duration (Table 1). A 1-month window will be permitted for each follow-up study interaction (\pm 15 days of exact due date).

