PGx testing will be completed using the GatorPGx panel, which is already available for clinical use in the CAP/CLIA certified UF Molecular Pathology Laboratory. Once results are entered into the EHR, Clinical Decision Support Best Practice Advisories already built into Epic will alert providers if a PGx interaction

might occur with a medication they prescribe. All clinical medication decisions will be made at the discretion of the healthcare provider.

Feasibility data collection:

The primary feasibility outcome will be change in patient treatment satisfaction between baseline and 6 months after PGx testing. This patient reported outcome will be measured via the Treatment Satisfaction Questionnaire for Medication (TSQM). The TSQM is a validated tool that assesses three medication-related domains (effectiveness, side effects, and convenience) to synthesize a global satisfaction score.^{5,6} Both global satisfaction and scores from individual domains will be analyzed.

Table 1. Proposed outcomes/measures to be tested

Outcome/Measure	Data source/Instrument	Ascertainment method	Baseline	3 mo.	6 mo.
Implementation Outcomes					
Treatment satisfaction	Treatment Satisfaction Questionnaire for Medication (TSQM)	Online or by phone	X	X	X
Medication adherence	Adherence Questionnaire	Online or by phone	X	X	X
Perceived value	Patient reported value	Online or by phone	X	X	X
Time discussing meds w/ healthcare provider	Patient reported estimate	Online or by phone	X	X	X
Effectiveness Outcomes					
Medication changes	EHR data	EHR data pull	X		X
Provider encounters	EHR data	EHR data pull	X		X
Socioeconomic Measures					
SEI	Patient report	Online or by phone	X		
Occupation	Patient report	Online or by phone	X		
Education level	Patient report	Online or by phone	X		
Household Income	Patient report	Online or by phone	X		
Household zip code	Patient report	Online or by phone	X		

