Analysis plan. For Aim 1, implementation outcomes such as prescriber acceptance, turnaround time, and cost will be assessed using descriptive statistics. Differences in patient reported outcomes such as treatment satisfaction, perceived value, and effectiveness outcomes (Table 1) will be initially compared between baseline and 6 months using Student's t-test or Mann-Whitney U test, depending on the data distribution. In addition to univariate analyses, multiple regression models will also be completed for each outcome, adjusted for potential covariates, such as age, race, sex, clinic site, and Charlson Comorbidity Index. In all analyses, a two-sided $P \leq 0.05$ will be considered statistically significant, and all statistical analyses will be completed in R ver. 3.6.3.

For Aim 2, interview transcripts will be managed using data management software (e.g., Nvivo or Atlas.ti). Data will be thematically analyzed using the widely used constant comparative method.¹³ This systematic approach involves several coding steps including identifying concepts and assigning codes, 2) grouping categories of emergent themes, and 3) axial coding to identify thematic properties. To ensure similarities and differences between patients' experiences can be captured, data analysis will be segmented by group and triangulated with survey data collected from healthcare providers (via separate protocol). Triangulation of data between sources also enhances the validity of the findings.¹⁴ Multiple coders, trained in the CCM approach, will conduct the analysis to ensure rigor. Meetings will be held to compare independent coding, discuss differences in interpretation, collapses analyses, and continuously refine the codebooks. Codebooks will be developed with each stakeholder group dataset. Once codebooks are finalized and analyses complete, each analysis will be validated by an additional coder analyzing a subset of the transcripts from each group.¹² Operational and thematic memos will be maintained across data collection and analysis to ensure researcher reflexivity, thematic saturation, and rich description of themes.

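### The primary baseline to 6-month comparison is within patients, but the plan names independent-sample tests for it

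*Combined protocol and SAP*

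**What the plan says.** Section 6 (Study population and setting) describes a single group: "Overall, we plan to recruit 100 patients from targeted clinics". Under Study design, the questionnaires "will be administered at baseline, and then again at 3 months and 6 months after PGx results are entered into the EHR", so the same people answer each time. Section 5, Aim 1 frames feasibility as a comparison of data "before and 6 months after PGx testing". Under Feasibility data collection the endpoint is a change: "The primary feasibility outcome will be change in patient treatment satisfaction between baseline and 6 months after PGx testing".

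The Analysis plan for Aim 1 then says that patient-reported outcomes and the effectiveness outcomes of Table 1 "will be initially compared between baseline and 6 months using Student's t-test or Mann-Whitney U test, depending on the data distribution". The criterion for all analyses is that "a two-sided $P \leq 0.05$ will be considered statistically significant". After these initial tests, "multiple regression models will also be completed for each outcome, adjusted for potential covariates, such as age, race, sex, clinic site, and Charlson Comorbidity Index". Nowhere does the plan mention a paired test, a signed-rank test, a repeated-measures analysis or a mixed model.

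**The concern.** Every 6-month score has a baseline partner from the same patient. An independent-sample test treats 100 baseline and 100 follow-up values as coming from 200 unrelated people. Its standard error then contains the variation between patients, which cancels in a within-patient change. If the two scores are positively correlated, p-values tend to be too large, intervals are too wide, and a real change is more likely to be missed. One sentence of the plan governs the primary outcome and the other before/after outcomes, so all of them are affected.

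Dropout adds a second problem. An unpaired test can take in every enrolled patient at baseline but only those who respond at 6 months. If dissatisfied patients leave, mean satisfaction rises with no change in anyone.

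The plan intends to use these results to support wider implementation and to inform the design of a larger trial. That trial would need the SD of the within-patient change, which an unpaired analysis does not estimate.

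**Working it through.** The plan has no power or sample-size calculation, so there is no figure of its own to reproduce.

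**Inputs from the plan:** n = 100 patients, two-sided alpha 0.05, one cohort measured repeatedly.

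**Assumed, because the documents are silent:** equal SDs (set to 1), correlation ρ between baseline and 6 months of 0 to 0.7, a true change d of 0.25 or 0.30 SD, and complete pairs except where stated.

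**Formulas (normal approximation)**
- Standard error used by the unpaired test: √(2/n) = √0.02 = 0.1414.
- True standard error of the mean change: √(2(1−ρ)/n).
- True type I error of the unpaired test: 2[1 − Φ(1.96/√(1−ρ))].
- True power of the unpaired test: Φ[(d/√(2/n) − 1.96)/√(1−ρ)].
- Power of the paired test: Φ[d/√(2(1−ρ)/n) − 1.96].
- Half-width of the 95% interval: 1.96 × standard error.
- Change detectable with 80% power, from each test's own standard error: (1.96 + 0.842) × standard error.

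**Worked case, ρ = 0.5, d = 0.30**
- Type I error: 1.96/√0.5 = 2.77, which gives 0.0056.
- Unpaired power: (0.30/0.1414 − 1.96)/0.7071 = (2.121 − 1.96)/0.7071 = 0.228, which gives 59%.
- Paired power: true standard error √(1/100) = 0.10, and 0.30/0.10 − 1.96 = 1.04, which gives 85%.

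| | ρ = 0 | ρ = 0.3 | ρ = 0.5 | ρ = 0.7 |
|---|---|---|---|---|
| True type I error, unpaired | 5.0% | 1.9% | 0.56% | 0.03% |
| Power at 0.30 SD, unpaired | 56% | 58% | 59% | 62% |
| Power at 0.30 SD, paired | 56% | 72% | 85% | 97% |
| Power at 0.25 SD, unpaired | 42% | 41% | 39% | 36% |
| Power at 0.25 SD, paired | 42% | 56% | 70% | 90% |
| 95% half-width, unpaired (SD) | 0.28 | 0.28 | 0.28 | 0.28 |
| 95% half-width, paired (SD) | 0.28 | 0.23 | 0.20 | 0.15 |
| Detectable at 80%, unpaired formula (SD) | 0.40 | 0.40 | 0.40 | 0.40 |
| Detectable at 80%, paired (SD) | 0.40 | 0.33 | 0.28 | 0.22 |

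With 80 pairs, ρ = 0.5 and d = 0.25, power is 30% unpaired and 61% paired.

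**Simulation check** (100 normal pairs, 10,000 runs; 3,000 for the signed-rank test)
- At ρ = 0.5 with no change, the rejection rates were 0.6% (unpaired t), 0.6% (Mann-Whitney), 5.0% (paired t) and 5.4% (signed-rank).
- At d = 0.30 they were 58%, 56%, 84% and 82%, in the same order. The rank tests behave like their parametric counterparts.

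**Dropout, with no true change.** Assume that 50% drop out in the lowest quarter of month-3 scores and 10% elsewhere.
- Overall dropout: 0.25 × 0.50 + 0.75 × 0.10 = 20%.
- The standard normal density at the lower quartile is 0.318. Completers' mean month-3 score is therefore raised by 0.318 × (0.90 − 0.50)/0.80 = 0.159 SD.
- Their 6-month mean is raised by 0.159 times the correlation between months 3 and 6. For correlations of 0.3, 0.5, 0.7 and 0.8 this is 0.05, 0.08, 0.11 and 0.13 SD. That is the false rise when all baselines are set against completers.
- The paired change is biased only by 0.159 times the difference between the month 3 to month 6 correlation and the baseline to month 3 correlation. It is zero if they are equal and 0.03 SD if they differ by 0.2.

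**The case against.** The strongest reply has five parts.

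1. *Student's t-test is also the name of the paired form, and the endpoint is called a change.* True. For the t-test, the unpaired reading is an inference from the test named beside it. That does not help the rank branch, because Mann-Whitney has no paired form. The choice between branches is left to the data, and the same sentence covers satisfaction scores and counts.
2. *The error is mainly conservative.* This stands. With positive correlation and no selective dropout there are fewer false positives, not more. Only a negative correlation reverses this: at ρ = −0.2 the type I error is 7.4%.
3. *The size is assumed.* This also stands. The loss is nil at ρ = 0 and moderate at 0.3. The plan specifies no confidence intervals, so the interval figures apply to any interval built on the same unpaired method.
4. *The dropout bias is a missing-data matter and seldom yields a false significant result.* In part. The plan defines no analysis set, so comparing all baselines with completers is one possible reading. In simulations of the scenario above under seven correlation settings, the unpaired t-test rejected in 2.8% to 5.1% of trials in five settings. It rejected in about 8% in the two where months 3 and 6 were much more strongly correlated than baseline and month 3; there the paired test reached 6%. The shift in the estimate remains.
5. *This is a pilot, the paired data are collected anyway, and regression follows.* The paired data do make the repair easy. But the plan sets a significance threshold and intends to act on the results. The covariates it names are patient characteristics, and it gives no change score, baseline term or patient effect, so the regression does not restore the pairing.

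**Conclusion.** The concern holds. The design is paired, and the tests as written are for independent samples: beyond doubt for Mann-Whitney, and on the natural reading for the t-test. If ρ is 0.3 to 0.7, all 100 pairs are complete and SDs are equal, the nominal 5% test operates at between 1.9% and 0.03%. It gives up about 14 to 36 percentage points of power for a 0.3 SD change (72 − 58 and 97 − 62, before rounding), and the interval is 1.20 to 1.83 times as wide as it need be. Under the dropout pattern assumed above, comparing all baselines with completers adds a false rise of about 0.05 to 0.13 SD, against 0.00 to 0.03 SD for the paired change. These sizes depend on correlations and dropout that the documents do not give; the mismatch between design and test does not. Because it affects the primary analysis, it must be corrected before the data are analysed.

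**What to change.** In the Analysis plan for Aim 1, replace the two named tests with a paired t-test or a Wilcoxon signed-rank test on the within-patient change. Apply this to TSQM and to every other baseline versus 6-month outcome. Report the mean (or median) change with its 95% confidence interval, the SD of the change, and the number of patients with both measurements.

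Make the adjusted models consistent with this. Either regress the change, or the 6-month value with baseline as a covariate, on the listed covariates; or fit a mixed model with a patient random effect. For questionnaire outcomes the mixed model can use baseline, 3 and 6 months and so keep patients with partial follow-up.

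The cost is one sentence for the tests and one for the regression. The schedule, the data collected and the number of patients stay as they are.

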An important secondary outcome assessing efficacy will include the number of medication changes within the 6-month follow-up period. Medication changes will be defined as the addition, removal, or dosage change to any PGx medication or medication within the same drug class. Comparisons of this outcome should estimate differences in trial-and-error drug dosing that is traditionally used in practice. These outcomes are important because if the results suggest that preemptive PGx testing is associated with increased patient treatment satisfaction, a reduction in medication changes, or increased perceived value of PGx testing, these findings would support expanded clinical implementation in medically underserved patients. This might also suggest that PGx could be further used as a tool to minimize disparities in pharmacotherapy. Other secondary outcomes that will be analyzed include: The prescriber acceptance rate of PGx EHR alert recommendations, number of encounters with a healthcare provider over the study period, genotype turnaround time, and estimated time spent discussing medications with a healthcare provider. These outcomes will be used to assess feasibility and will inform design of a large clinical trial to be funded by future grants.

Socioeconomic data collection: We have previously observed significant associations between calculated geographic access scores and rate of PGx drug prescriptions, which considerably strengthened in subanalyses by race. Whether this association is exclusively related to geography and race or whether it is also related to socioeconomic determinants is unknown. Thus, we will test whether socioeconomic status is a social determinant of health related to PGx drug usage. Patients will answer survey questions related to their education, employment, and income (Table 1).

Qualitative data collection: An estimated sample size of 20 patients from the 100 recruited participants will be recruited for this aim. Patient sampling will be aimed at achieving an approximately even distribution of sex (male and female) and race (Latino and black).

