Qualitative data collection will follow a sequential explanatory approach^{8,9} to expand on findings from the quantitative analyses of patient survey data in Aim 1. Following the initial study visit, patients will be asked to provide additional consent for participation in an in-depth, semi-structured, audio-recorded phone interview expected to take 20-30 minutes. They will receive additional compensation for participation. A semi-structured script will be developed with interviewers trained by a qualitative method expert.

Interviews will explore patients' perspectives on implementation outcomes associated with the intervention to identify best practices in three key areas: 1) factors (barriers and facilitators) impacting willingness to undergo PGx testing; 2) preferences for the overall testing process (to identify strategies to improve upon intervention adoption and sustainability); and 3) preferences for the delivery of results, including best provider-patient communication approaches (and related challenges) as well as practices for sharing results (e.g., with other providers or family). Thematic findings have emerged in samples of 15-20 participants.^{10,11} An estimated sample of 20 participants will be recruited, but recruitment will end once thematic saturation has been attained. Data analysis of transcribed interviews and data collection will be concurrent to ensure thematic saturation can be met.¹²

Subject Compensation: Subjects will receive compensation for the time required for questionnaire completion. They will receive \$20 (cash or gift card) upon completion of the baseline survey and another \$20 upon completion of the 6-month survey. Subjects who complete a semi-structured interview will receive another \$20 upon interview completion.

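### The primary within-patient change in TSQM is assigned tests that are not stated to be paired, one of them for independent samples, and the 3-month scores and missing 6-month surveys have no stated handling

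*Combined protocol and SAP*

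**What the plan says.** Section 5 (Aim 1) and Section 6 describe a single group of 100 patients, measured before and after testing. Under Feasibility data collection in Section 6: "The primary feasibility outcome will be change in patient treatment satisfaction between baseline and 6 months after PGx testing".

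Under Study design, questionnaires "will be administered at baseline, and then again at 3 months and 6 months after PGx results are entered into the EHR". Table 1 marks four surveys at all three visits: TSQM, adherence, perceived value, and time discussing medications.

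The Aim 1 part of the Analysis plan says that patient-reported outcomes "will be initially compared between baseline and 6 months", and that this is done "using Student's t-test or Mann-Whitney U test, depending on the data distribution". It then adds that "multiple regression models will also be completed for each outcome, adjusted for potential covariates". The covariates are listed, but no time point, baseline term or within-patient structure is given. The significance threshold is a two-sided P of 0.05.

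No section gives the 3-month scores a role, defines an analysis set, or says what happens when the 6-month survey is missing. The window of 15 days either side covers late surveys, not absent ones. Subject Compensation states payments for the baseline survey and "upon completion of the 6-month survey", and none for the 3-month survey.

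On use of the results, Section 6 says that if testing is associated with, among other things, higher satisfaction, "these findings would support expanded clinical implementation in medically underserved patients". It closes the list of outcomes with "These outcomes will be used to assess feasibility and will inform design of a large clinical trial".

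**The concern.** A change measured in the same patients calls for a paired analysis. Mann-Whitney U treats the two sets of scores as coming from different people, and Student's t-test does the same unless it is specified as paired. If the scores look non-normal, the plan's own rule leads to a test that does not match its primary outcome. A real improvement could then be missed, and the reported P-value would not have its nominal meaning.

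The second gap concerns loss to follow-up. The surveys are answered online or by phone, so some missing 6-month scores are to be expected. The text does not say whether patients without a 6-month score are dropped, kept on the baseline side only, or handled through their 3-month score. These choices can give different answers from the same data. The result is meant to support wider implementation, so the choice should be fixed before the data are seen.

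**Working it through.** **Inputs.** From the documents: n = 100, one group, two-sided alpha 0.05, surveys at 0, 3 and 6 months. The documents give no power calculation, effect size, SD, within-patient correlation or dropout rate. There is therefore no planned figure to reproduce, and everything below rests on assumed values. Scores are in SD units, with equal SD at each visit.

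**Step 1: pairing, no missing data.** Let r be the correlation between baseline and 6 months.

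- Unpaired SE = sqrt(2/n) = sqrt(2/100) = 0.141.
- Correct SE of the mean change = sqrt(2(1 - r)/n). At r = 0.5 this is sqrt(1/100) = 0.100.
- True type I error of the unpaired test = 2[1 - Phi(1.96/sqrt(1 - r))]. At r = 0.5: 1.96/0.707 = 2.77, giving 0.0056.
- Power of the unpaired test for a change d = Phi[(d/0.141 - 1.96)/sqrt(1 - r)]. At d = 0.3, r = 0.5: (2.12 - 1.96)/0.707 = 0.23, giving 59%.
- Power of the paired test = Phi[d/SE - 1.96]. At d = 0.3, r = 0.5: 3.00 - 1.96 = 1.04, giving 85%.

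| Assumed r | True type I error, unpaired | Power at 0.3 SD, unpaired | Power at 0.3 SD, paired |
|---|---|---|---|
| 0.3 | 1.9% | 58% | 72% |
| 0.5 | 0.56% | 59% | 85% |
| 0.7 | 0.03% | 62% | 97% |

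Simulation of the rank tests at r = 0.5 agrees. Mann-Whitney U has a type I error below 1%, and its power is about 56% against 83% for Wilcoxon signed-rank.

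**Step 2: missing 6-month surveys.** Trials of 100 patients were simulated with trivariate normal scores, no true change and 20% lost at 6 months. Loss was logistic, with an odds ratio of 2 or 3 per SD of its driver. Visit correlations were all 0.5, all 0.7, or 0.7 between adjacent visits with 0.5 from baseline to 6 months. The model is maximum likelihood on all three visits without covariates. Ranges cover the six settings. False improvement means a significant result in the favourable direction, nominally 2.5%.

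| Loss follows | Paired completers: bias (SD); false improvement | All baselines against available 6-month scores: bias (SD) | Model with 3-month score: bias (SD); false improvement |
|---|---|---|---|
| Worsening from 0 to 3 months | +0.05 to +0.12; 8-19% | 0.00 to +0.05 | within 0.001; 2.3-2.7% |
| Low 3-month score | about 0; near nominal | +0.06 to +0.13 | about 0; near nominal |
| Low unseen 6-month score | +0.04 to +0.09; 7-14% | +0.13 to +0.19 | +0.06 to +0.13; 9-23% |
| Worsening to unseen 6 months | +0.10 to +0.19; 21-43% | +0.05 to +0.09 | +0.07 to +0.13; 10-26% |

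A two-sample test restricted to completers has the same bias as the paired test but a larger SE. In the first row its false improvement is 0.2-4.1%, so an unpaired reading is not always conservative once data are missing.

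**Step 3: limits of the model.** Its SE is 0.96 to 1.01 times that of the paired test, so it gains almost no precision. In the first row, a bias of +0.01 to +0.03 SD remains if 30% skip the 3-month survey at random, and +0.03 to +0.09 SD if all lost patients leave before 3 months.

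**The case against.** The strongest reply is that the primary outcome is already defined as a change in one group, so a competent analyst would run the t-test paired. On that view, Mann-Whitney U is a slip for signed-rank. This is a fair reading of the t-test. It does not rescue the other branch, where the plan names an independent-samples test, and it leaves the regressions and missing surveys unaddressed.

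A second reply is that this is a pilot with an illustrative simulation behind the criticism, and that the leading dropout scenario fits poorly. The 6-month survey is paid and no payment is stated for the 3-month one, so patients may skip month 3 rather than month 6. That stands, and it limits what the 3-month score can offer. The pilot nonetheless plans a significance test and attaches an implementation message to it.

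Three stronger readings are tempting, and the documents do not support them:

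- A reader might infer that collecting a 3-month score without testing it, or choosing 6 months as the endpoint, is an error. The plan consistently sets the contrast at baseline against 6 months, and that is a legitimate choice.
- A reader might infer that the planned result will be biased toward improvement. No dropout rate or reason for loss is given. With complete data the unpaired error is conservative.
- A reader might infer that a mixed model must be the primary analysis. It does better than paired completers under two of the four mechanisms, about the same under one, and worse when loss follows the unseen 6-month score.

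**Conclusion.** The point holds. Its firm part is the mismatch between a within-patient primary outcome and tests that are unpaired or not stated to be paired. That follows from the text alone. Its size depends on the assumed correlation: with complete data and correlations of 0.3 to 0.7, the unpaired type I error is about 1.9% down to 0.03% instead of 5%. At 0.3 SD and correlation 0.5, roughly 26 to 27 percentage points of power are lost (85 - 59 = 26 for the t-test, 83 - 56 = 27 for the rank tests).

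The secondary part is a real but smaller gap: no stated use of the 3-month scores and no rule for a missing 6-month survey. The bias figures are illustrations at 20% loss under assumed mechanisms, not estimates for this trial. A model using the 3-month score removes the bias when loss depends on observed scores, for patients who answered at 3 months. It does not do so when loss depends on unseen scores. The change should be made, but it does not call the design into question.

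**What to change.** 1. In the Aim 1 part of the Analysis plan, state that baseline against 6 months is a within-patient comparison. Use a paired t-test or, for non-normal changes, the Wilcoxon signed-rank test in place of Mann-Whitney U. Make the regressions within-patient as well, and define the analysis set.
2. Prespecify a repeated-measures mixed model on baseline, 3 and 6 months (categorical visit, unstructured covariance), reporting the 6-month minus baseline contrast with a 95% CI. It may be the primary analysis with the paired test as sensitivity, or the reverse, provided the choice is made before the data are seen. State the role of the 3-month score for the other three surveys: the same model where the scale allows, otherwise descriptive.
3. Report survey completion at each visit, and add a delta-shift sensitivity analysis. At 20% missing, each 0.5 SD shift in the missing patients moves the estimate by 0.20 x 0.5 = 0.10 SD. This shows sensitivity to the missing-at-random assumption but does not test it.

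The cost is a wording change and slightly more analysis work in standard R, with no new data or visits. The drawback is that the model depends on missing-at-random, which the observed data cannot confirm, and its 3-month score gives no help for patients lost before 3 months. Reporting both the paired test and the model guards against relying on either alone.
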